Study protocol cover page

Official study title: Multicenter registry to study the characteristic and outcomes of Jordanian Heart Failure patients

The Jordanian Heart Failure Registry (JoHFR)

NCT04829591

The actual document date and approval date 30/3/2021

The updated document date 17/4/2021

A Multicenter Registry to Study the Characteristics and Outcomes of Jordanian Heart Failure Patients. The Jordanian Heart Failure Registry (JoHFR)

ClinicalTrials.gov Identifier: NCT04829591

(Study protocol)

Principal investigator and study chair : [name] , MD , MSc , FACC , FSCAI .

Principal investigator: [name].

Brief Summary

Heart Failure research registry is a collection of computerized information about individuals with heart failure. The database in this registry is obtained from several Jordanian medical centers which will represent an extremely valuable resource for epidemiological research on heart failure patients.

Detailed Description:

Understanding the cause of Heart Failure (HF) and how the body will respond to it, is critical for an effective treatment. HF is a global problem with significant morbidity and mortality, despite improved understanding of the pathophysiology and a growing range of therapeutic options. Jordanian Heart Failure Registry (JoHFR) will be the first research project of heart failure prevalence in Jordan. It is undertaken by primary healthcare professionals with main aim to improve knowledge about the care of patients with HF. The investigators responsible for conducting this research are physicians and their teams who deal with heart failure patients in their outpatient and inpatient clinic centers including the public and private medical sectors in Jordans' medical community . Standards in the Hashemite kingdom of Jordan complies with the recognized good guideline directed medical practices internationally.

Objectives of the registry:

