Up to date, there is still a lack of reliable pathology data that summarizes patient cases with heart failure disease. This research aims to fill this gap and provide the local and international medical communities with this important set of comparative data in order to determine our current situation in regards to screening, management, and follow up of patients. This will have a direct impact on improving Heart Failure patient outcomes by directing our focus on strengths and weaknesses in our management in this ongoing high morbidity and mortality syndrome. Furthermore, this registry will focus on describing the diagnostic and therapeutic approaches undertaken by cardiologists in their care of patients with HF in order to improve future management

of patients with high HF risks. The prevalence of the clinical profiles of patients with acute and chronic HF will also be evaluated.

Study design and methodology:

- This registry consists of multiple variables including demographics, concomitant diseases, diagnostic procedures, hemodynamics, laboratory data, and medications used, discharge information and instructions. The patient information is detailed in the attached questionnaire (appindex1) which will be filled by participating who will record details of their HF patients and transfer these data for documentation.
- This study aims to include sufficient number of patients with Heart Failure and is expected to last for extended time until the study sample is completed by participating healthcare professionals. The data collected at 12 months will be the basis of the initial statistics, upon which the trial duration will be determined.
- The principal research coordinator and his team will train personnel of the participating units on how to register patients and how to use the registry.
- Patient safety, security and confidentiality will be retained at all times during the course of the study and thereafter.

• Follow up after one year should include data on morbidity (including Heart failure hospitalization) and mortality with detailed information on medications, quality of life, and functional capacity. • The study will comply with the ethics of research and (IRB) institutional review board approvals and any other required official organizational requirements.

Inclusion and exclusion criteria:

- Inclusion criteria:
 - 1. Patients who are 18 years or older with Heart Failure diagnosis as defined by internationally recognized guidelines.

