 - 2. Current residents of the Hashemite Kingdom of Jordan.
- Exclusion criteria:
 - 1. Patients who refuse or unable to sign a consent form.
 - 2. Patient inability to follow up with provider

Statistical analysis:

Data will be pooled and descriptive and comparative statistical tests will be used to categorize the patients based on the disease sub-typing and management quality and to find the prevalence of heart failure disease different types, classes and stages amongst Jordanians. Furthermore, comparative analysis will be performed to test the efficiency, accuracy, and the quality of medical practice in Jordan. Statistical analysis will be done using SPSS V21. See appindex1 below.

Annindex1.

	Patient Initials/Site number:
DOB: / / (MM/DD/YYYY) Gender: M F Admission date/ Office visit / / :	
Discharge Date/Time / / :	

Medical History (Select all that apply):

□ H/O ASCVD	Implanted devices	□ Notes :
□ H/O Arrhythmias	History of structural heart disease	
	Other relevant medical history	
□ ASCVD risk factor:		
🔷 🕹 DM		
ITN		
Smoking		
Alcohol Abuse		
🔷 🗘 Dyslipidemia		
Obesity		
 Positive family history of premature ASCVD 		
🔷 🗘 CKD		
Others.		
	Heart Failure History	
Etiology:	□ Ischemic/CAD	Non-Ischemic
Check if history of :		Hypertensive
		Alcohol/Other Drug
		Chemotherapy
		□ Viral
		Postpartum

	□ Familial
	Other Etiology
	Unknown/Idiopathic

Known history of HF prior to this admission?	⊖ Yes	o No
--	-------	------

# of hospital admissions in past 6 mo./office visit for HF:	0	2 >2	o Unknown
	Medications Used Prior t	o Admission: [Select all that ap	oly]

Symptoms	Dyspnea		Palpitations
(Closest to Admission) Select all that apply	NYHA class (, , , V) ❑ Orthopnea	 PND Fatigue Chest pain 	

Vital	signs

(Closest to Admission/Office visit)

Heart Rate	Heart Rate bpm	□ Reg □ irreç	
Examination	JVP: O Yes	0 No	
(Closest to Admission/Office visit)	Rales: o Yes	o No	
	Lower Extremity o Yes Edema	• No	
Lipids	TC: LDL: HDL: _ mg/dL mg/dL	TG: mg/dL	□ Lipids Not Available
Labs Closest to Admission)/ office visit	Na	⊖ mg/dL	□ Unavailabl e
	BNP	⊖ ng/L	□ Unavailabl e
	К	⊖ mg/dL	□ Unavailabl e
	Hb	⊖ g/dL	□ Unavailabl e
	Albumin	⊖ g/dL	□ Unavailabl e
	NT-proBNP	⊖ ng/L	□ Unavailabl e
	SCr	⊖ mg/dL	□ Unavailabl e

eGFR	 ○ ml/min/ 1.73m² 	
BUN	⊖ mg/dL	□ Unavailabl e
Troponin (Peak) ng/L �� T quantitative / Hs �� I	NormalAbnormal	□ Unavailabl e
Ferritin ng/mL		
Transferrin saturation HbA1C %	Unavailable	

Fasting Blood Glucose (mg/dL)	Unavailable
EKG QRS	Unavailable

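### The Etiology row asks for history rather than cause, gives no one-or-several rule, and no item on the form records the primary cause of heart failure

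*Protocol*

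**What the plan says.** The Heart Failure History block of Appendix 1 has a row labelled Etiology with the instruction "Check if history of". The options are Ischemic/CAD and a Non-Ischemic column: Hypertensive, Alcohol/Other Drug, Chemotherapy, Viral, Postpartum, Familial, Other Etiology and "Unknown/Idiopathic". The row carries neither a select-one nor an all-that-apply instruction.

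The separate history block is headed "Medical History (Select all that apply" and collects ASCVD, its risk factors, alcohol abuse and structural heart disease, among others.

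The Detailed Description says: "Understanding the cause of Heart Failure (HF) and how the body will respond to it, is critical for an effective treatment". The Statistical analysis section plans to "categorize the patients based on the disease sub-typing and management quality". A second aim stated in that section is "to find the prevalence of heart failure disease different types, classes and stages amongst Jordanians".

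**The concern.** In a descriptive registry the form is the measuring instrument. Here the label and the instruction of one item ask different questions. One site may follow the label and tick the cause it judges responsible. Another may follow the instruction and tick every listed condition the patient has had. A patient with coronary disease and hypertension would then get one tick at the first site and two, one in each branch, at the second. Pooled, the column mixes two variables, and nothing in the record shows which one a given tick represents.

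At stake is any statement about the main cause of heart failure in this population, in particular an exclusive ischemic versus non-ischemic split, and any comparison of that split between sites or with other registries.

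**Working it through.** The protocol states no expected etiology distribution, so there is no figure to reproduce. The check is a comparison of wording, followed by a test of what tick-box data can and cannot yield.

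**Wording, side by side (all in Appendix 1)**

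| Item | What it asks | Response rule |
|---|---|---|
| Etiology, label | cause of heart failure | none |
| Etiology, instruction | history of the condition | none |
| Medical History | history | all that apply |
| Symptoms; prior and in-hospital medications | presence or use | all that apply |
| Primary Cause of Death | one main cause, then a sub-class | asks for the primary cause |

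Three things follow.

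1. The form gives an all-that-apply rule on several items and gives none here, so the response rule for Etiology is undefined.
2. The form asks for a primary cause in the case of death but not in the case of heart failure.
3. If the row is read as history, a tick for Ischemic/CAD or Alcohol/Other Drug largely repeats Medical History. If it is read as cause, it is new information. The record does not show which reading was used.

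**What the ticks can yield**

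Let I be the share ticked Ischemic/CAD, N the share ticked for at least one named non-ischemic cause, and B the share ticked for both. Four exclusive groups always exist:

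- ischemic only = I − B
- non-ischemic only = N − B
- both = B
- neither or unknown = 1 − I − N + B

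They sum to 1, and patient-level records give B exactly. Without those records, B lies between max(0, I + N − 1) and min(I, N).

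An illustration on assumed shares, which are not in the documents: I = 60% and N = 50%.

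- The two shares add to 60 + 50 = 110%.
- B lies between 60 + 50 − 100 = 10% and 50%.
- With B = 10%, the groups are 50, 40, 10 and 0, total 100%.
- With B = 50%, the groups are 10, 0, 50 and 40, total 100%.

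So a distribution can be reported. The primary-ischemic share cannot be fixed: it is 60% if every double-ticked patient is called ischemic, and 60 − B if none is. That is 50% when B = 10% and 10% when B = 50%. The width of this interval is B itself, and the choice within it depends on a rule.

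**Whether a later rule repairs it**

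An analysis plan can pre-specify a hierarchy for double ticks, which yields a single category per patient. It cannot supply the physician's view of the cause if that was never recorded, nor tell a tick meaning past history from one meaning cause. That would require going back to the charts.

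**The case against.** The strongest reply is that the row does ask for cause. It is labelled Etiology, and options such as Postpartum, Familial and "Unknown/Idiopathic" make sense only as causes. History is collected elsewhere, so this row may well have been meant differently. The table was also damaged in extraction, so the exact placement of the instruction and the box style cannot be relied on. This shows that the causal reading is reasonable. It does not remove the printed instruction, which asks for something else, and the absence of a primary-cause item does not depend on layout.

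A reader might infer stronger things, which the documents do not support:

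- *That several boxes are expressly allowed.* The row does not say so; it is silent.
- *That no etiological distribution can be produced.* Multiple-response shares and the four exclusive groups are both available.
- *That the protocol promises an exclusive ischemic split and cannot deliver it.* The word types is undefined in the Statistical analysis section. The objectives mention acute and chronic heart failure and the form collects ejection fraction, so types may mean something other than etiology. The sentence on cause is background.
- *That the overlap can be sized by multiplying comorbidity shares*, for example 50% coronary disease × 55% hypertension = 27.5%. Those shares are assumptions, independence is assumed, and treating comorbidity as an etiology tick presupposes the history reading that is in dispute.

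It is also fair to say that a hierarchy for double ticks may stand in an analysis plan that is not shown, and that a forced single cause would discard real mixed etiology. The first does not recover an uncollected judgement. The second is met by a contributing-causes line.

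**Conclusion.** The point holds as a defect of data definition. The Etiology row is labelled as cause, instructs for history, sets no response rule, and has no primary-cause item beside it. A single primary cause for patients ticked in both branches therefore depends on a rule the protocol does not state, and the meaning of each tick may differ between sites.

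The size is unknown. The documents give no etiology shares, and the recruitment aim is only this: "This study aims to include sufficient number of patients with Heart Failure". Neither the proportion nor the number of patients affected can therefore be derived. The conclusion rests on the wording as it survives in the extracted form, and on the assumption that no separate completion guide already settles how the row is filled in. It should be corrected, because the change is cheap before data collection and laborious afterwards, but it does not undermine the registry as a whole.

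**What to change.** In Appendix 1, replace the instruction in the Etiology row with *Primary cause of HF (select one)*, keeping Other Etiology and Unknown/Idiopathic among the options. Add a second line, *Contributing causes (select all that apply)*, so that mixed etiology is kept. Leave comorbidities in Medical History. Explain the difference in the site training that the Study design and methodology section already provides for. Report etiology from the primary-cause item, with contributing causes as multiple-response percentages. A separate valvular box is optional, since Other Etiology can hold it.

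The cost is one reworded item, one added line and a short training note. The downside is a small judgement by the treating physician when causes coexist. For patients already registered on the present form, the primary cause would have to be taken from the chart, or their etiology reported only as the four exclusive groups and marked as collected under the old wording.

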	Duration (ms)			
	EKG QRS Morphology	Normal	RBB B VCD	PacedUnavailable
Procedures				

No Procedures	Atrial Fibrillation Ablation or Surgery
Cardiac Cath/Coronary Angiography	Cardiac Valve Surgery
Coronary Artery Bypass Graft	□ Cardioversion
CRT-P (cardiac	CRT-D (cardiac resynchronization therapy
resynchronizationtherapy pacing only)	with ICD 🖵 Intra-aortic Balloon Pump
 Dialysis or Ultrafiltration ICD only 	Left Ventricular Assist Device
Mechanical Ventilation	Pacemaker
Right Cardiac Catheterization	

EF	- By Echo - By other means %	Obtained:	 This Admission Within the last year > 1 year ago
Added Oral Medications during hospitalization Select all that apply	□ None □ ARNI □ ARB	 Aldosterone Antagonist Hydralazine Nitrate 	 ACE Inhibitor Beta Blocker
Parenteral Therapies during hospitalization Select all that apply	 None Dopamine Iron Milrinone 	 Nitroglycerine Other IV Vasodilator 	 Dobutamine Loop Diuretics Intermittent Bolus Continuous Infusion

Was the patient ambulating at the end of hospital day 2?	Yes No	Not Documented	
---	--------	----------------	--

Was DVT prophylaxis initiated by the end of hospital day 2?	Yes No	Contraindicated
---	--------	-----------------

lf yes,	 Low dose unfraction Low molecular (LMWH) Warfarin Other 		 Factor Xa Inhibitor Direct thrombin inhibitor Intermittent pneumatic compression devices (IPC)
Discharge Date/Time / / :	1		MM/DD/YYYY only
Primary Cause of Death	 Cardiovascular 	Non-Cardiovascular	 O Unknown
If Cardiovascular:	 Acute Coronary Syndrome 	 ○ Worsening Heart Failure 	 Sudden Death Other
When is the earliest documen measures only?	tation of comfort	Day 0 or 1 Day 2 or after	 Timing unclear Not Documented

Symptoms (closest to discharge)	WorseUnchanged	Better, Symptomatic Better, Asymptomatic	Una Una	able to determine
Vital Signs (closest to Discharge)	Weight ᡇ	₩¥¥¥		ot Documented
	Heart Rate Bpm regula	r Irregular	□ N	ot Documented
	BP-Supine _ / _ mmHg (systolic/diastolic)	□ N	ot Documented
	Respiratory Rate breaths	s per minute		
Exam (Closest to Discharge)	JVP:○ Ye	s o No	o Unknow n	
	Rales: o Yes		0 1	lo

	Lower Extremity o Yes Edema	0 N	10
Labs (Closest to Discharge)	Na	∘ mg/dL	Unavailable

BNP	o mg/dL	🗅 Unava	ailable
SCr	o mg/dL	🗅 Unava	ailable
BUN	o mg/dL	🗅 Unava	ailable
NT-BNP (pg/mL)		ot Documente	ed
κ _ο mEq/L	o mmol/L	∘ mg/dL	
eGFR	** N 1.7:		MDRD

Angiotensin Converting Enzyme Inhibitor (ACEI)		
Prescribed?	∘ Yes ∘ No	Frequency:
If Yes, Medication: Dosage:		
Beta-Blocker		

Name:	Dose:		

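### As legible, Appendix 1 prints inconsistent or implausible units for BNP, sodium and potassium, and its prior-admission count can be read in two ways

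*Protocol*

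**What the plan says.** The protocol's Study design and methodology section makes the attached questionnaire (Appendix 1) the instrument that participating clinicians fill in. The Statistical analysis section then states: "Data will be pooled and descriptive and comparative statistical tests will be used". What the form prints is therefore what gets analysed, across all sites together.

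Three lab labels matter, as far as the form can be read:

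- **BNP:** ng/L in the labs closest to admission or office visit; mg/dL in the labs closest to discharge.
- **Sodium:** mg/dL in both blocks.
- **Potassium:** mg/dL only in the admission block; in the discharge block a choice of "mEq/L o mmol/L ∘ mg/dL".

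The Heart Failure History part also has one count item, "of hospital admissions in past 6 mo./office visit for HF", with a single set of answer options that runs up to more than two. No separate count of office visits is legible.

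No section gives a conversion rule for the labs or a definition for the count.

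**The concern.** A unit printed on a collection form tells the site what to write and the analyst how to read it. If one analyte carries two incompatible units at two time points, or a unit in which laboratory results would be implausible, some sites will convert to the label and others will copy their laboratory's number. The stored value alone does not show which was done.

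The count raises a different problem. The Detailed Description says the registry draws on both inpatient and outpatient settings, so clinic patients with several visits and no admission are to be expected. If one site counts admissions and another counts admissions plus visits, a stable patient with three clinic visits can fall in the same top category as a patient with three HF admissions. Prior HF admission is an obvious descriptor of severity, and it would then mean different things at different sites.

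**Working it through.** The protocol states no figure on this point, so there is nothing to reproduce. The check is unit arithmetic plus a side-by-side reading of labels. The atomic masses (K 39.10, Na 22.99) are physical constants and are not in the protocol. The example concentrations are illustrative.

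**BNP**
- 1 mg = 10^6 ng and 1 dL = 0.1 L, so 1 mg/dL = 10^6 × 10 = 10^7 ng/L.
- An admission value of 500 ng/L is 500 / 10^7 = 0.00005 mg/dL.
- If 300 ng/L at discharge were written as 300 under the mg/dL label and taken literally, the ratio to an admission value of 500 ng/L would be 300 × 10^7 / 500 = 6,000,000. The discharge label cannot be meant literally.

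**Potassium**
- For a monovalent ion, mEq/L equals mmol/L, so three labels give two scales.
- mg/dL = mmol/L × 39.10 / 10 = mmol/L × 3.91.
- 4.0 mmol/L = 15.6 mg/dL. Conversely, 4.0 read literally as mg/dL is 4.0 / 3.91 = 1.02 mmol/L.
- Over an illustrative 3.5 to 5.0 mmol/L, the mg/dL values run from 13.68 to 19.55. The two ranges do not overlap, so a typical value usually betrays its scale.

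**Sodium**
- mg/dL = mmol/L × 22.99 / 10, so 140 mmol/L = 321.9 mg/dL. The label is the same at both times, so it is implausible rather than inconsistent. A site that writes 140 under it contradicts the label; a site that converts writes about 322.

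**NT-proBNP (no error)**
- Admission uses ng/L and discharge uses pg/mL. 1 pg/mL = 1 ng/L, so the values are directly comparable.

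**Count item: two readings set side by side**

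| Reading of the slash | What is counted | Patient with 0 admissions and 3 HF office visits |
|---|---|---|
| Marks the index contact | HF admissions in the six months before this admission or office visit | 0 |
| Joins two events | HF admissions plus HF office visits | more than 2 |

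The first reading has support: elsewhere the form uses the same slash for the setting of the index contact (the admission or office-visit date, the examination block, the lab block). Nothing on the form excludes the second. Both answers are valid options, so no range check separates them.

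**The case against.** **The units may be damaged by extraction, and range checks would repair most errors.** The lab tables are visibly broken, each unit follows a radio-button symbol, and a lost option cannot be ruled out. That is why the point is stated as legible and should be confirmed on the original form. It is less likely that extraction turned ng/L into mg/dL. The range-check argument largely stands: no plausible BNP result would be taken as mg/dL, and the two potassium scales rarely overlap. A ticked discharge potassium unit can also be converted. This limits the harm but leaves the labels wrong.

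**No planned analysis depends on it.** The Statistical analysis section names classification, prevalence of types, classes and stages, and quality of practice. It names no admission-to-discharge change. That is correct and keeps the point minor. Laboratory data are nonetheless among the variables the registry lists, and they will be pooled.

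**Training will settle it.** The protocol promises training on registering patients. Training could fix a reading of the count, but no such rule is written, and training does not correct a printed unit.

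**A reader might infer that the form combines two counts in one field.** The protocol does not show this. Given how the form uses the slash elsewhere, the admissions-only reading is at least as plausible. The label is ambiguous, and no more than that is claimed.

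**A reader might also infer a date-format error**, because the form asks for "MM/DD/YYYY only" while the cover page is day first ("The actual document date and approval date 30/3/2021"; "The updated document date 17/4/2021"). The protocol does not support this. The form's legible format labels agree with each other, and the cover dates are administrative. On the 2021 calendar, 132 of 365 dates (36%) become a different valid date if day and month are swapped, but that is only the share that could be swapped, not an expected error rate. The smallest such shift is 27 days, so swapping one date of a stay shorter than that gives a negative stay or one of at least 27 days, which a simple check would flag. The admission and first follow-up dates show no format label, but a different date style is a preference, not a correction.

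**Conclusion.** The point holds, and it is minor. As legible, the BNP labels contradict each other by a factor of 10^7, the sodium label is implausible at both times, and the potassium labels span two scales 3.91-fold apart. Values under these labels are not comparable between admission and discharge, or across pooled sites, without guessing the unit; for many gross errors a range check would make that guess safe.

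The count item is the smaller drafting fault but the harder one to repair: if sites read it differently, the answers cannot be separated after entry. How many sites would do so is unknown, and the protocol gives no basis for an estimate.

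The conclusion assumes that the legible unit labels match the original form and that no conversion rule or item definition exists outside the protocol. No sample size, power or error rate is affected.

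**What to change.** 1. Print one unit per analyte, identical in the admission and discharge blocks: BNP in ng/L, sodium and potassium in mmol/L. Remove the other potassium options, and carry the same units into the database.
2. Reword the history item to: *HF hospital admissions in the 6 months before this admission/office visit*. Add a separate item, *HF office visits in the same 6 months*, only if the registry wants that count.
3. If data have already been entered, query potassium and sodium values by site against both scales, and ask each site how it read the count item.

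Items 1 and 2 cost label edits on the form and the database, and at most one extra item. Item 3, where it applies, costs a round of site queries. No date-format change is needed on this ground.

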	Aldosterone Antagonist		
	Medication: Dosage:	Frequency:	
Anti-hyperglycemic Medications:			
Name:	Dose:		
Lipid Lowering Medication(s):			
Name:	Dose:		
Hydralazine Nitrate			

Name:	Dose:
	Other Medications at Discharge
☐ Antiarrhythmic ☐ Amiodarone ☐ Sotalol ☐ Other	 Ca Channel Nitrate Blocker Ranolazine Digoxin Other Anti-Hypertensive Diuretic Other Loop Diuretic Thiazide Diuretic

Angiotensin Receptor Blocker (ARB)				
Name:	Dose:			
Angiotensin Receptor Neprilysin Inhibitor (ARNI)				
Name:	Dose:			
	Acetylsalicylic acid (ASA)			
Name:	Dose:			
	Anticoagulation Therapy			
Prescribed?	Yes No	Dosage		
lf Yes,	Class:			

Warfarin	

Clopidogrel		
Prescribed?	∘ Yes ∘ No	

If Yes,	Dosage: Frequency:		
	Other Antiplatelet(s)		
Name:	dose:		
Activity	\circ Yes \circ No Diet (Salt restricted)	∘ Yes	∘ No
Follow-up	\circ Yes \circ No Medications	∘ Yes	• No
Symptoms Worsening	\circ Yes \circ No Weight Monitoring	∘ Yes	o No
Follow-up Visit Scheduled	 ○ Yes ○ No Date/Time of first follow up visit: 	//:	-
Location of first follow-up vis	i t: �� Office Visit �� Home Health Visit	TelehNot Doc	

Medical or Patient Reason for no follow-up		• No	
appointment being scheduled	 Yes appointment being scheduled? 		
	Follow up visits form:		
Scheduled at:	3 months 6 months	12 months	
NYHA class: (, , , V)			

eGFR:			
Loop diuretics (name,dose):			
Vital signs			
	New EF ,method, if a	ny :	
CV related hospital admission:	C Yes:	□ Yes:	G Yes:
	□ WHF		□ WHF
		□ WHF	□ ACS □ Arrhythmias
	Arrhythmia		
	S	Arrhythmia	No
		S	
	Others	□ Others	12 months

No	
3 months 6 months	

Labs:	
Meds:	

Other notes:

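### The follow-up form records cardiovascular admission as yes/no with a cause tick but no date or number, and puts all drugs except loop diuretics under one unstructured entry, so admission counts, exact timing and detailed medication data cannot be reliably obtained

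*Protocol*

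**What the plan says.** Under Study design and methodology, the protocol sets the content of follow-up: "Follow up after one year should include data on morbidity (including Heart failure hospitalization) and mortality", and this is to come "with detailed information on medications, quality of life, and functional capacity". The same section makes the appendix the data specification: "The patient information is detailed in the attached questionnaire".

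The last part of Appendix 1 is headed "Follow up visits form" and has columns for 3, 6 and 12 months. The fields that bear on this point are:

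- **Admissions.** One item, "CV related hospital admission", with yes or no in each column. Under yes there are cause boxes: worsening HF, "ACS □ Arrhythmias" and others. No label for a date or a number of admissions appears.
- **Drugs.** One row reading "Loop diuretics (name,dose", and further down an entry labelled only Meds.

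Two earlier parts of Appendix 1 collect more. The baseline part asks how many HF admissions there were in the past 6 months, with answer bands up to more than 2 and an unknown option. The discharge part has a separate block for each of several drug classes, including ACE inhibitor, beta-blocker, aldosterone antagonist, hydralazine nitrate, ARB and ARNI, most with space for name and dose.

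**The concern.** The registry exists to describe the outcomes of HF patients and the quality of their care. The questionnaire is where those data are fixed. A statistical analysis plan, if there is one, can choose how to analyse what was recorded, but it cannot recover a date, a count or a drug that no field asked for.

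Two things are at stake. First, repeat HF admissions within a visit interval collapse into a single yes. The follow-up data then cannot be set against the pre-enrolment count from the baseline form, and an admission can be placed only within a 3- or 6-month window. Second, drug treatment at one year feeds the comparison of medical practice announced under Statistical analysis. If a class is absent from an unstructured entry, the analyst cannot tell whether the patient was off it or the site left it out, and the answer may differ from site to site.

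**Working it through.** **Step 1. What the methods text asks for against what the form holds.** The protocol states no event rate, sample size or omission rate, so there is no planned figure to reproduce. The main check is field by field.

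| Information | Follow-up form | What can be derived |
|---|---|---|
| Any HF admission | Yes/no with a worsening-HF box, three visits | Proportion with at least one, per interval and by 12 months |
| Number of admissions | No visible field | Not obtainable; the baseline part does ask for it |
| Date of admission | No visible field | Interval only; exact time lost |
| Loop diuretic | Name and dose | Obtainable |
| All other drug classes | One Meds entry | Depends on what each site writes |

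**Step 2. How much a count of ticked intervals could fall short.** This matters only if the ticks are used as a count or rate. All inputs are assumptions except the visit times. Each box is taken to cover the time since the previous visit (the form states no look-back period), so the intervals t are 0.25, 0.25 and 0.50 years. The true rate r is taken as 0.3 or 0.6 HF admissions per patient-year, with everyone followed for the full year.

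Poisson admissions: expected ticks = Σ [1 − exp(−r t)].

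- r = 0.3: 2(1 − e^−0.075) + (1 − e^−0.15) = 0.1445 + 0.1393 = 0.284. Shortfall (0.300 − 0.284)/0.300 = 5%.
- r = 0.6: 2(1 − e^−0.15) + (1 − e^−0.30) = 0.2786 + 0.2592 = 0.538. Shortfall (0.600 − 0.538)/0.600 = 10%.

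Admissions clustered in some patients, as gamma frailty with variance 2: expected ticks = Σ [1 − (1 + 2 r t)^(−1/2)].

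- r = 0.3: 2(1 − 1.15^−0.5) + (1 − 1.3^−0.5) = 0.1350 + 0.1229 = 0.258. Shortfall 14%.
- r = 0.6: 2(1 − 1.3^−0.5) + (1 − 1.6^−0.5) = 0.2459 + 0.2094 = 0.455. Shortfall 24%.

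The loss grows with the rate and with clustering, because both put more than one admission into the same interval.

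**Step 3. The drug entry.** Suppose 70% of patients are truly on a class at one year, and the entry omits it for 10% to 20% of those taking it. If an unlisted class is coded as not taken, the recorded figure is 0.70 × 0.90 = 63% down to 0.70 × 0.80 = 56%. If it is coded as unknown, there is no fixed downward shift, but the analyst is left with missing data that cannot be told apart from true non-use. The 70% and the omission rates are again assumptions.

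**The case against.** A reader might infer that the form cannot deliver one-year morbidity at all. The documents do not support that. Cause is ticked at all three visits, so the proportion with at least one HF admission by one year can be derived, and that meets the wording on HF hospitalization. The protocol promises no admission rate, no recurrent-event analysis and no all-cause admissions. Nor is time to first HF admission beyond estimation: yes/no status at 3, 6 and 12 months is interval-censored data, for which standard methods exist. Only exact timing is lost. All of this stands.

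It is also fair that drugs are not confined to one free-text line, since loop diuretics have their own row. The discharge part is not a perfect model either: as the text reads, the beta-blocker, ARB and ARNI blocks show only name and dose, so a blank there is ambiguous too. A wholly empty Meds entry would be recognisable as missing; the ambiguity lies in a class left out of an entry that was filled in. Persistence on a drug class is not a stated aim.

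Finally, the table is visibly broken by extraction from PDF. The Meds entry may have a cell per visit, and a write-in space after yes may have been lost. But no label for a date or number survives anywhere on the form, and none is visible for drug classes other than loop diuretics.

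What remains after these concessions is the lack of a count and a date, and a medication entry that falls short of the detail the methods text asks for.

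**Conclusion.** The point holds in limited form. The follow-up form supports a one-year yes/no HF-admission outcome and an interval-censored time to first admission. It does not support a number of admissions, although the baseline form asks for one, or exact timing. For drugs other than loop diuretics, it does not reliably deliver the detailed information that the protocol says follow-up should include.

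The undercount figures of 5% to 24% illustrate what happens if ticks are read as a count; they are not estimates for this registry, because the rates and the frailty variance are not in the documents. The drug figures of 63% and 56% apply only if an unlisted class is coded as not taken. The conclusion itself rests on the form as it can be read, not on any of these figures. It is worth correcting because data not captured at a visit would afterwards have to be sought in charts across public and private sites.

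**What to change.** Revise the follow-up page of Appendix 1:

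- At each visit, record the number of admissions since the last contact and, for each one, the date and cause. State that the look-back runs from the previous contact.
- Replace the Meds entry with rows for the drug classes already on the discharge form, each answered yes, no or not recorded, with name and dose. The three-way answer is the essential part; copying the discharge blocks as they stand would carry over the ambiguity of a blank.

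The cost is one revised page and a few more minutes per visit. Visits already completed on the present form would keep the less detailed data and should be flagged as such in the analysis. While the page is open, the sponsor could also check mortality and quality of life: the methods text asks for both, and no follow-up field for either is visible. That is a separate point from this one.
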